## 9. BIOMARKER, CORRELATIVE, AND SPECIAL STUDIES

### 9.1. Collection of Specimen(s)

The primary hypothesis of the correlative component to this trial is that biomarkers of sensitivity and resistance to MEK inhibition can occur through ERK-dependent and ERK-independent pathways. To test this hypothesis we propose correlative studies on research biopsies acquired at these time points 1) in all patients prior to trametinib monotherapy (mandatory) 2) all patients after progression on Part 1 with trametinib (mandatory) 3) all patients at time of progression on trametinib combined with GSK2141795 (optional). In addition, archival FFPE sections, plasma and a whole blood samples will be collected..

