#### 9.2.1.2. Reverse Phase Protein Assay (RPPA)

In addition to IHC, we will plan to perform other methods of assessing protein levels such as RPPA. This assay will be run by MD Anderson Cancer Center RPPA-Functional Proteomics Core Facility, website below:

<http://www.mdanderson.org/education-and-research/resources-for-professionals/scientific-resources/core-facilities-and-services/functional-proteomics-rppa-core/index.html>

Sections of the OCT embedded core biopsies will be evaluated by a pathologist to verify tumor content. Tissue will then be cut out of the OCT and protein will be extracted using standard methods. The protein will be denatured, diluted and arrayed on nitrocellulose coated slides. The slides will be probed with a set of 150 validated antibodies (including antibodies to proteins being analyzed by IHC) and spot density determined by MiroVigene software. Samples will be normalized for protein loading and concentrations will be determined using the Super Curve Fitting program. Supervised and un-supervised hierarchical clustering analysis will then be performed. This data will be compared to results derived by IHC and used to determine differences in protein expression between patients that respond to treatment and those that do not. Proteins of interest that are included in this assay are; PTEN, PI3KCA, Cyclin D1 and total and phosphorylated forms of AKT, 4E-BP1, p70-S6, ERK and MEK.

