#### 9.2.1.3. Quantitative Targeted Absolute Proteomics (QTAP)

If sufficient biopsy material is available, we will also evaluate changes in expression or phosphorylation levels of key protein kinases using QTAP. This assay will be performed in the laboratory of [name] at the University of North Carolina School of Medicine. The QTAP/MRM technique has been previously used to quantitatively define TNBC oncogenic kinome signatures in human cell lines, mouse xenograft models and human tumor biopsy samples. When comparing non-treated samples to those treated with a targeted MEK inhibitor, this assay was also able to mechanistically define kinome reprogramming and potentially predict combination therapies to overcome resistance.

QTAP is an LC/MS technology that uses multiplexed Multiple Reaction Monitoring (MRM) for the absolute quantitation of targeted peptides. Protein

lysates will be made from the flash frozen core biopsies collected pre-treatment and at the time of progression and analyzed as previously described. In brief, lysates will be passed through columns of kinase inhibitor-conjugated beads to isolate protein kinases. After several washes, bound proteins will be eluted and digested with trypsin. Digested peptides will then be labeled with iTRAQ and separated by a Tempo LC MALDI Spotting System. Data obtained from the MALDI TOF/TOF will be processed with the ProteinPilot software to identify proteins from databases searches and the Paragon Algorithm software will be used to quantify changes in bound kinase levels. Human cell lines and mouse xenograft tumors were used in pre-clinical studies to define kinome activation state and response to targeted kinase inhibition. Synthetic peptides with incorporated heavy isotopes (C, N-labeled arginine and lysine) serve as quantitative internal standards and can be made in phosphorylated and non-phosphorylated forms. The method will be multiplexed so many kinases (~25-50) can be monitored simultaneously. Main proteins to be included in kinome analysis include: EGFR, PDGFR, RAF, RAS, RSK, MEK, ERK, PTEN, P13K, AKT and MYC. Other proteins in the MAPK and PI3K pathways, cell cycle regulators, stress response, and receptor tyrosine kinases will also be included.

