### 9.2.2 Genome and Transcriptome Analysis

In conjunction with the [name] Laboratory ([name] and [name]; scientific collaborators, Boston, MA) we will perform massively parallel exome and transcriptome sequencing on tumor samples collected pretreatment. They have previously reported the development of a targeted, massively parallel sequencing approach to detect genomic alterations in 137 cancer genes from FFPE tumor samples. They used this approach to identify a novel genetic mechanism of resistance to the BRAF-inhibitor vemurafenib in a patient with metastatic melanoma who developed resistance after an initial dramatic response. More recently, they have performed whole exome sequencing on FFPE tumor and normal DNA from 15 patients with a wide variety of cancer types, including lung adenocarcinoma, prostate adenocarcinoma, leiomyosarcoma, and urothelial carcinoma.

In this project, they will employ unbiased, comprehensive studies of patient-derived breast tumor tissue to identify clinical mechanisms of response and resistance to trametinib and/or GSK2141795 in triple-negative breast cancer. To accomplish this, they will perform whole exome analysis using massively parallel sequencing, analyzing “sets” consisting of pre-treatment and post-progression samples (when applicable) together with corresponding matched normal DNA from blood samples on an estimated 18 patients with an initial clinical response (CR, PR) to trametinib monotherapy (n=9) or to trametinib combined with GSK2141795 (n=9). They will also sequence all of the mRNA transcripts (the transcriptome) in the frozen breast cancer samples from these patients. The processes for whole exome sequencing and whole transcriptome sequencing have been thoroughly validated by [name] in the laboratory of [name] of the Broad Institute.

ABL1	CTNNB1	IDH1	MYCL1	RET
ABL2	EGFR	IDH2	MYCN	RICTOR
AKT1	EPHA3	IGF1R	NF1	RUNX1
AKT2	EPHA5	IKBKE	NF2	RUNX1T1
AKT3	EPHB6	IKZF1	NKX2-1	SMAD2
ALK	ERBB2	JAK2	NOTCH1	SMAD3
APC	ERBB3	JAK3	NOTCH2	SMAD4
ATM	ERBB4	KDR	NOTCH3	SMARCA4
AURKA	FAM123B	KEAP1	NOTCH4	SMARCB1
BCL2	FBXW7	KIAA0774	NPM1	SMO
BRAF	FGFR1	KIAA1303	NRAS	SOCS1
BRCA1	FGFR2	KIT	NTRK1	SRC
BRCA2	FGFR3	KRAS	NTRK2	STK11
CCND1	FGFR4	MAP2K1	NTRK3	SUFU
CCNE1	FHIT	MAP2K2	PAX5	TCF4
CDC73	FKBP9	MAP2K4	PDGFRA	TERT
CDH1	FLT1	MCL1	PDGFRB	TET2
CDK4	FLT3	MDM2	PDPK1	TGFBR2
CDK6	FLT4	MDM4	PIK3CA	TNFAIP3
CDK8	FRAP1	MEN1	PIK3R1	TOP1
CDKN1A	GATA1	MET	PTCH1	TP53

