**RPPA:**

For each patient the protein intensity fold-change ratios will be calculated from the RPPA intensity values. Ratios between tumors sampled prior to initiating trametinib single agent treatment and at time of progression on either single agent trametinib or the combination (TOP/pre-treat ratio), will be calculated. These ratios will be median-centered and clustered using Cluster 2.0 software (<http://rana.lbl.gov/EisenSoftware.htm>). Student’s t-test for differences between average protein intensity ratios at these intervals will be calculated using Microsoft Excel by grouping all the ratios for individual clusters.

Table 4	Biomarker Prevalence				
	10%	20%	30%	40%	50%

HR	0.43	0.51	0.55	0.56	0.57
----	------	------	------	------	------

These results and exploratory analyses will be used in planning future studies of this

combination treatment regimen in this patient population. Biomarker analyses on required research biopsies at study entry will be conducted to assess the predictive value of PTEN and other biomarkers on patient outcome. For example, we will assess impact of PTEN status and other markers on survival outcomes as well as ORR and CBR. For survival-based outcomes, Table 4 shows detectable hazard ratios between marker groups for varying prevalence rates and at least 80% power. The Type I error constraint is quite lax in this setting, reflecting a phase II approach and relaxation of constraints but also in the univariate setting can be used to cast a wider net to capture potential markers of interest that may provide insights for the development of future biomarker-driven therapeutic strategies. Fisher exact tests will also be used to identify potential differences in ORR and CBR rates between biomarker groups as well, although depending on prevalence rates we will likely have sufficient power to only detect large differences (e.g. 35%) if we constrain Type I error to 0.05. Again, these will be largely exploratory, and lack of significant results will be viewed with caution given these limitations but will provide

**Table 1: Statistical Considerations for Biomarker Analysis.** Maximum detectable hazard ratios (HR) using one-sided log-rank test with 80% power and alpha=0.2, assuming a sample size of 37, 26 months accrual and 12 months follow-up.

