insights into potential relationships and mechanisms. To assess mechanisms of acquired resistance, research biopsies will be conducted at time of progression on trametinib monotherapy and at time of progression to the combination of trametinib and GSK2141795. Restaging will

occur after every 2 treatment cycles (8 weeks).

Whole exome and transcriptome sequencing:

Genetic alterations from whole exome sequencing data would be tabulated. Data analysis will be conducted in collaboration with computational biologists in the [name] lab / Broad Cancer Program computational group. Whole exome sequencing data will be analyzed for base substitutions, small insertions and deletions, copy number alterations, and loss of heterozygosity. Selected alterations of interest will be validated by Sanger sequencing or related orthogonal technologies in use in the [name] lab. Data will be compiled to generate a catalogue of candidate genomic alterations that cause resistance to MEK and ATK inhibition. Genes listed above in Section 9, Table 3 will be the first to be examined as well-known genes related to cancer growth and survival. Molecular alterations of known significance will be reported. Molecular alterations of unknown significance will also be presented; however, assessment of the clinical significance will be investigated by *in vitro* studies (i.e. site-directed mutagenesis, growth inhibition analysis, immunoblot studies, and kinase assays).. Identified markers of interest will be explored in relation to several clinical outcomes of interest for each treatment component. Specifically, we will look at incidence of mutations and marker expression levels similar to that described above, where we will first look graphically at associations with objective response as well as with progression-free survival. Model-based evaluations may also be used in an exploratory manner to better assess these relationships in a quantitative manner, but will be limited given the sample size available for these analyses.

QTAP/Kinome assay:

D=Difference in log 2 scale	1.00	1.58	2.00	2.32
Fold change (2 D )	2	3	4	5
Power (%)	8.93	81.69	97.39	99.61

Table 5 summarizes the power to detect a true difference of D with a sample size of 9 patients in each group (pre and post treatment)

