For the QTAP/Kinome assay: Paragon Algorithm software will be used to quantify changes in bound kinase levels. As seen in Table 5, a two-sided paired sample t-test will have at least 80% power to detect a 3-fold change in bound kinase levels before and after treatment with 9 patients in each group (assuming Type I error of 0.05). Based on preliminary data, we assume that 100 kinases are captured, of which 10% of them are truly differentially expressed between pre- and post- treatment and a common standard deviation of 0.95 (in log2 scale, Table 5). Given the limited paired sample size, nonparametric tests will be used (i.e. Wilcoxon signed rank test) if approximate normality is not achievable through transformation.

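### The RPPA and kinome comparisons of pre-treatment with progression biopsies are not split by prior benefit, so they cannot separate acquired resistance from drug exposure in tumors that were resistant from the start

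*Combined protocol and SAP*

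**What the plan says.** - **Purpose.** Section 13.4 (Correlative endpoints): "To assess mechanisms of acquired resistance, research biopsies will be conducted at time of progression on trametinib monotherapy".
- **Who is biopsied.** Section 9.1 lists "all patients after progression on Part 1 with trametinib (mandatory"; there is no condition on earlier response. The biopsy at progression on the combination is optional.
- **RPPA.** Section 13.4: "For each patient the protein intensity fold-change ratios will be calculated from the RPPA intensity values". The ratio compares progression, on either regimen, with the sample taken before trametinib. The t-test is done "by grouping all the ratios for individual clusters". Response does not enter it. Section 9.2.1.2 says the RPPA data will also be used for "differences in protein expression between patients that respond to treatment and those that do not".
- **Kinome.** Section 9.2.1.3 uses "flash frozen core biopsies collected pre-treatment and at the time of progression", if there is enough tissue. Section 13.4 claims at least 80% power "to detect a 3-fold change in bound kinase levels before and after treatment with 9 patients in each group". It does not say which 9 patients.
- **Sequencing.** Section 9.2.2 limits the paired exome work to "18 patients with an initial clinical response (CR, PR) to trametinib monotherapy (n=9" and 9 responders to the combination.
- **Status.** Section 13.4 calls all correlative analyses descriptive and exploratory. Section 13.1 names intrinsic and acquired resistance as separate ideas. No section defines either one or says how to tell them apart in the data.

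**The concern.** Acquired resistance means that a tumor was controlled and then escaped. A tumor that grows through the first 8-week restaging was probably resistant at baseline. The difference between its two biopsies shows what drug exposure did to it, not how it became resistant.

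If both kinds of patient contribute to one mean change, two errors are possible. A change confined to patients who first benefited is diluted and may be missed. A change that occurs only in patients who never benefited can reach significance and be taken for a resistance mechanism. Section 13.4 says the exploratory results will inform future studies of the combination, so the interpretation matters even though no decision rule of this trial depends on it.

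**Working it through.** **Inputs.** From Section 13.4: 9 pairs, two-sided paired t-test, SD 0.95 (log2), 3-fold change D = 1.58, stated level 0.05, 100 kinases of which 10% truly change, and Table 5 power of 8.93, 81.69, 97.39 and 99.61% at 2-, 3-, 4- and 5-fold. From Section 13.3: ORR 5% (null) and 20% (alternative), 37 patients.

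**1. Reproduce Table 5.** The noncentral t has 8 df and noncentrality D√9/0.95. At a per-test level of 0.05, power is about 79% at 2-fold and 99.1% at 3-fold, which does not match. Reading 0.05 as a false discovery rate, solve

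0.9α / (0.9α + 0.1 × power) = 0.05.

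This returns all four entries exactly. At 3-fold, α = 0.00478 and power = 81.69%. Check: 0.9 × 0.004777 = 0.00430; 0.1 × 0.8169 = 0.08169; 0.00430/(0.00430 + 0.08169) = 0.05. Both thresholds, 0.0048 and 0.05, are carried forward.

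**2. Dilution.** Let a share f of pairs carry the full 3-fold change and the rest none:

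- pooled mean = f × 1.58
- between-patient variance = 0.95² + f(1 − f) × 1.58²

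At f = 0.20 the mean is 0.316 log2, which is 2^0.316 = 1.24-fold. The SD is √(0.9025 + 0.16 × 2.4964) = 1.14. Power with 9 pairs, simulated from this mixture:

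| Share carrying the change | Pooled fold change | Power, p<0.0048 | Power, p<0.05 |
|---|---|---|---|
| 100% | 3.0 | 82% | 99% |
| 60% | 1.93 | 15% | 52% |
| 40% | 1.55 | 5% | 26% |
| 20% | 1.24 | 1% | 10% |
| 5% | 1.06 | 0.5% | 5% |

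The 5% and 20% rows are the plan's own response rates. The 40-60% rows are an assumption for the case where stable disease before progression also counts as benefit; the documents give no rate for it.

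**3. The reverse case.** A 3-fold change only in the 80% who did not respond averages 0.8 × 1.58 = 1.264 log2, or 2.4-fold. With 9 pairs it is detected with 40% power at 0.0048 and 81% at 0.05. Where non-responders are the majority, the pooled test is more sensitive to their change than to the responders' change.

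**4. What responder-only pairs would give.** Expected responders are 37 × 0.05 = 1.85 to 37 × 0.20 = 7.4. Seven pairs give 42% power at FDR 5%; nine give 81.7%. The chance of at least 9 responders among 37 at 20% is 31%.

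**5. What nine kinome pairs allow as a comparison.** With 7 prior-benefit and 2 primary-progression pairs, a two-sample t-test for a 3-fold difference (7 df) has 43% power at 0.05 and 10% at 0.0048.

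**The case against.** The strongest reply is that treatment-induced change is a legitimate target. Section 9.2.1.3 presents the kinome assay as a way to define reprogramming under MEK inhibition, and for that purpose all pairs are useful. This stands, and it is why the pooled analysis should be kept.

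A reader might infer that the plan will report every pre/progression change as acquired resistance. The documents do not say so. Acquired resistance is the stated purpose of the biopsies, but the RPPA and kinome test descriptions do not use the term. A reader might also infer that the kinome test pools every progressor. It does not: it is planned on 9 pairs, tissue permitting. The gap is that their selection is unstated. Nine is also the number of monotherapy responders budgeted for sequencing, but nothing links the two.

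Section 9.2.1.2 does plan a responder/non-responder comparison of RPPA data. That is a partial answer. It concerns protein expression and is not carried into the ratio test of Section 13.4. The plan to relate markers to response and PFS is placed under sequencing.

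The arithmetic has limits too. It covers the kinome only, and the 0.0048 threshold is back-solved. The 80% share of non-responders is not a lower bound: the alternative is an ORR of at least 20%, and 9 responders of 37 would be 24%. Non-response is also not the same as intrinsic resistance, since a patient with stable disease may later acquire resistance.

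**Conclusion.** The point holds as a gap in the analysis plan. Biopsies taken to study acquired resistance come from all Part 1 progressors. The RPPA ratio test has no split by prior benefit and the kinome test has no selection rule, while the same protocol restricts paired sequencing to initial responders. A pooled change cannot be attributed to acquired resistance.

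The loss can be large, but its size is illustrative: it assumes no change in one group, a uniform 3-fold change in the other, and unselected kinome pairs. None of these assumptions is in the documents, and no figure here quantifies RPPA. The analyses are exploratory and no endpoint or decision rule is affected, so this is a worthwhile improvement and not a threat to the trial's main conclusions.

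**What to change.** In Section 13.4:

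1. Keep the pooled pre/progression analysis and describe it as treatment-associated change.
2. Classify every pair, leaving no gap: prior benefit (CR, PR, or SD at one or more restagings before PD) or primary progression (PD at or before the first restaging). Use Part 1 response for pairs ending at monotherapy progression and Part 2 response for pairs ending at combination progression.
3. Report RPPA change within each group and the difference between groups. Describe a change as a candidate for acquired resistance only if it is larger in prior-benefit pairs.
4. State before assay how the 9 kinome pairs are chosen. If all are prior-benefit patients, there is no comparison group: report the change alone and do not attribute it to acquired resistance from the kinome data alone.

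The cost is SAP wording. Response is already assessed every 8 weeks, and no new samples or assays are needed. The downside is smaller groups. The split makes the results interpretable but does not restore 80% power, so they remain exploratory.

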**Correlative endpoints:**

The statistical analysis corresponding to the correlative studies will be descriptive and exploratory in nature.

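### Kinome power (Section 13.4): the text says Type I error 0.05, but Table 5 shows power at a 5% false discovery rate; a minor labelling error in an exploratory analysis

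*Combined protocol and SAP*

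**What the plan says.** The QTAP/Kinome paragraph of Section 13.4 makes this claim: "a two-sided paired sample t-test will have at least 80% power to detect a 3-fold change in bound kinase levels". The comparison is pre-treatment against post-treatment samples, and the sample size and error rate behind the claim are stated as "with 9 patients in each group (assuming Type I error of 0.05". The paragraph adds two planning inputs. One is the number of kinases and the share that change: "we assume that 100 kinases are captured, of which 10% of them are truly differentially expressed between pre- and post- treatment". The other, for the variability on the log2 scale, is "a common standard deviation of 0.95". The fallback is that "nonparametric tests will be used (i.e. Wilcoxon signed rank test) if approximate normality is not achievable through transformation".

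The Table 5 caption reads: "Table 5 summarizes the power to detect a true difference of D with a sample size of 9 patients in each group". The table gives D = 1.00, 1.58, 2.00 and 2.32 (2-, 3-, 4- and 5-fold) with power 8.93, 81.69, 97.39 and 99.61%.

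The paragraph names no false discovery rate and no multiplicity procedure. Two other places limit its weight. Section 13.4 says that the statistical analysis of the correlative studies "will be descriptive and exploratory in nature". Section 9.2.1.3 makes the assay conditional: "If sufficient biopsy material is available, we will also evaluate changes in expression or phosphorylation levels of key protein kinases using QTAP". Section 9.2.1.3 also puts the number of kinases that can be monitored together at about 25 to 50, not 100.

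**The concern.** A paired t-test with 9 pairs and a mean change of about one SD should not have only 9% power at a two-sided 0.05. The first cell of Table 5 therefore does not fit the stated error rate. The share of kinases truly changed is another sign: a power calculation for one test at a fixed level has no use for it, whereas an FDR calculation needs it.

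What is at stake is how the kinase list is produced and read. An analyst who follows the text could test every kinase at 0.05 without adjustment and accept a much larger share of false hits than the table was built on. A reader of the table would conclude that 2-fold changes are almost undetectable, although the test as described has about 79% power for them.

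**Working it through.** **Inputs** (Section 13.4 and Table 5): two-sided paired t-test, n = 9 pairs, df = 8, SD 0.95 (log2), 100 kinases of which 10% are changed, D as tabulated.

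**Noncentrality**, with 0.95 as the SD of paired differences: D / (0.95/√9) = D / 0.3167, which gives 3.16, 4.99, 6.32 and 7.33.

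**Step 1: the plan's figures.** For each D, find the per-kinase threshold a that solves 0.9a / (0.9a + 0.1 × power(a)) = 0.05, and take power(a) from the noncentral t distribution.

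| Fold | Threshold a | Power at 5% FDR | Table 5 | Power at 0.05 |
|---|---|---|---|---|
| 2 | 0.000522 | 8.93% | 8.93% | 78.95% |
| 3 | 0.004777 | 81.69% | 81.69% | 99.11% |
| 4 | 0.005695 | 97.39% | 97.39% | 99.98% |
| 5 | 0.005825 | 99.61% | 99.61% | >99.99% |

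Check at 3-fold: 0.9 × 0.004777 = 0.00430; 0.1 × 0.8169 = 0.08169; 0.00430 / 0.08599 = 0.050.

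**Step 2: other readings.** None of these gives the printed row.
- Independent measurements with 0.95 at each time point (SD of differences 0.95 × √2 = 1.34), level 0.05: 50.1, 86.9, 97.3, 99.4%.
- Bonferroni, 0.05/100: 8.66, 40.37, 70.09, 86.37%.
- One-sided 0.05: 89.08% at 2-fold.
- Two-sample t, 9 per group, level 0.05: 55.49, 91.14, 98.69, 99.81%.

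No single fixed level can give the row, because the implied level changes with D. Nor can a different SD at 0.05: the four cells would need 4.58, 1.45, 1.34 and 1.31. A 10% FDR with 5% changed gives the same numbers, since both require a/power = 1/171. The plan states 10% changed, so the FDR is 5%.

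**Step 3: false share if each kinase is tested at 0.05.** With 100 kinases, expected false hits are 90 × 0.05 = 4.5. Expected true hits are 10 × 0.7895 = 7.895 (2-fold) or 10 × 0.9911 = 9.911 (3-fold). The expected false share, taken as expected false hits over expected hits, is 4.5/12.395 = 36% or 4.5/14.411 = 31%; it is also 31% at 4- and 5-fold. The table rests on 5%.

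With 25 or 50 kinases and 10% changed, expected false hits are 22.5 × 0.05 = 1.1 or 45 × 0.05 = 2.3. The share is unchanged, because the count cancels. It does depend on the 10%: if 5% or 20% were changed (our assumption), it would be 49-55% or 17-20%.

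**Step 4: a concrete FDR procedure.** Table 5 comes from the solved equation in Step 1, not from a named procedure. Simulating Benjamini-Hochberg at 5% (20,000 runs, 100 independent kinases, 10 changed by the same fold, normal data) gives 17.1, 79.6, 96.9 and 99.5% for the t-test. For the Wilcoxon fallback the smallest two-sided p with 9 pairs is 2/512 = 0.0039. At least 0.0039 × 100/0.05 = 7.8, so 8, of 100 kinases must reach it before any is declared, and power at 3-fold is about 26%. With 50 kinases the minimum is 4 and power about 38%. With 25 it is 2, and power is about 43% or 59% (2 or 3 changed).

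**The case against.** The best defence is that the table is calculated correctly and only its label is wrong or incomplete. The FDR inputs are printed beside it, so a statistician could infer the intent. The analysis is exploratory, depends on tissue, and drives no sample size or decision rule. The only power claim made in the text, for a 3-fold change, survives, and the text claims nothing for 2-fold. All of this stands and is why the point is minor. It does not remove the mismatch: the stated error rate and the stated power cannot both be right, and the text does not tell the analyst to control the FDR.

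Three stronger readings are tempting, and the documents do not support them.
- **Nine pairs are too few, or the 80% claim is false.** Power at 3-fold is 81.7% or 99.1%. The wording becomes marginally untrue only if Benjamini-Hochberg is adopted (about 79.6%), and the plan does not name that procedure.
- **The plan commits to unadjusted testing at 0.05 per kinase.** The text never says that the rate is per kinase. The 31-36% follows from that reading.
- **The 100 kinases contradict the 25-50 in Section 9.2.1.3.** The two figures may count different things, so this calls for reconciliation.

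Calling 0.95 a common SD is also not an error. It may mean common to all kinases, and a paired test needs the SD of differences. It is a clarification to make.

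**Conclusion.** The concern holds as a minor labelling error. Table 5 is the power at a 5% FDR with 10% of kinases truly changed, while the text attributes it to a Type I error of 0.05. At 0.05 per kinase the row would read 79, 99, >99.9 and >99.9%. Only the 2-fold cell moves materially, from 9% to 79%.

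The identification of the FDR rests on an exact match of all four cells from the plan's own inputs. The false share rests on the 10% assumption, an equal fold change in all changed kinases and the t-test. The simulated powers also assume independent kinases. The expected number of false hits (4.5, or about 1.1-2.3) depends on which kinase count applies; the share does not.

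**What to change.** Choose one.

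**(a) Name the FDR.** In the kinome paragraph and the Table 5 caption, replace the Type I error of 0.05 with a false discovery rate of 5%, assuming 10% of kinases truly changed. Keep Table 5 as it is and report FDR-adjusted p-values. If Benjamini-Hochberg is the procedure, add that simulated power is about 17, 80, 97 and 99.5% for 100 kinases, and change at least 80% to about 80%. Note that the Wilcoxon fallback has much lower power under FDR control. The cost is some wording, an adjustment step and fewer nominal hits.

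**(b) Keep 0.05 per kinase as an exploratory screen.** Say that it applies to each kinase, restate the row as 79, 99, >99.9 and >99.9%, and disclose an expected false share of about 31-36% for the t-test under the 10% assumption. The cost is wording and one table row; the drawback is the high false share, now visible.

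Under either option, state that 0.95 is the SD of paired log2 differences, and reconcile the 100 kinases in Section 13.4 with the 25-50 in Section 9.2.1.3. Neither option affects the number of patients or any decision rule.
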